Date: 01.01.2020

The Effect of Estradiol Valerate, Lng-IUD, and Micronized Progesterone Treatment On Health Quality of Patients with Heavy Menstrual Bleeding

Women who were admitted and treated for heavy menstrual bleeding were asked to participate in this comparative study. Women were eligible for entry if they had self-described heavy menstrual bleeding, had a regular cycle, had completed their family and were 40–50 years old at initial assessment.

After a thorough physical examination and ultrasonographic evaluation, all women underwent endometrial biopsy before the study by using a Pipelle endometrial suction curette to rule out any organic endometrial pathology. Blood samples were analysed to test for hemoglobin (Hb), hematocrit (Hct), ferritin, serum iron and iron-binding capacity and coagulation tests such as prothrombin time and activated partial thromboplastin time.

The study was approved by the Institutional Review Board and Local Ethics Committee. After they gave written informed consent, patients who fulfilled eligibility criteria were recruited to one of the following 3 groups:

Group 1: Women who were treated with estradiol valerate/dienogest regimen for heavy menstrual bleeding. 28 days of E2V/DNG was administered using a dynamic dosing regimen. (E2V 3 mg on days 1–2, E2V 2 mg/DNG 2 mg on days 3–7, E2V 2 mg/DNG 3 mg on days 8–24, E2V 1 mg on days 25–26 and placebo on days 27–28).

Group 2: Women who were treated with LNG-IUD for heavy menstrual bleeding. LNG-IUD is containing 52 mg levonorgestrel at initial placement and releases 20 microgram levonorgestrel per day. This is approved for 5 years of use by the US FDA for treatment of HMB.

Group 3: Women who were treated with oral Micronized Progesterone 200 mg for heavy menstrual bleeding. Cyclic, luteal-phase administration of progestin remained a widely used but little research treatment strategy for HMB for several decades.

None of the recruited patients were not prescribed oral iron preparations and patients who were symptomatic because of anemia (hb<10 mg/dl) were excluded.

Baseline characteristics of women are age (years), body mass index, parity, current smoker, days of bleeding, length of cycle (days), number of days of heavy bleeding, number of days of painful bleeding, unable to leave house on heaviest days, number of days housebound, number of nights disturbed, Pictorial Bleeding Assessment Chart (PBAC) score (A monthly score of 100 or more on this chart is significantly associated with heavy menstrual bleeding of more than 80 ml per cycle, as measured by the alkaline haematin method), endometrial thickness at time of treatment (mm), uterine size (length x width).

The Exclusion criteria are

1. ultrasound abnormalities (submucosal fibroids, intramural fibroids greater than 3 cm in diameter, large subserosal fibroids, endometrial polyps);
2. laboratory abnormalities (follicle stimulating hormone level higher than 40 iu/l, adverse endometrial histology)
3. hysteroscopic abnormalities (submucosal fibroids, endometrial polyps),
4. incidental adnexal abnormality on ultrasound,
5. severe intermenstrual bleeding, severe dysmenorrhoea, severe premenstrual pain, chronic pelvic pain,
6. medical contraindications to either study treatment,
7. previous endometrial ablation or resection,
8. uninvestigated postcoital bleeding
9. untreated abnormal cervical cytology.

10. pregnancy; lactation; occurrence of <3 menstrual cycles following childbirth, abortion or lactation;
11. current use of an intrauterine device; hypersensitivity to any of the study drug ingredients and known or suspected malignant or premalignant disease.
12. systemic diseases like hypertension, diabetes, thyroid diseases or coronary artery diseases; and history of previous medication for menorrhagia
13. using anticoagulant drugs

Women who were recruited the study will be assessed at 1,3 and 6 months with Hot Flush Rating Scale (HFRS), Menopause Rating Scale (MRS), menorrhagia multi-attribute scale (MM-AS), pictorial bleeding assessment chart and blood sample analysis.

The primary outcomes assessed

1. Hot flush rating scale: Measures included the HFRS, a self-report measure of frequency and problem rating of Hot Flushes/Night Sweats over the past week. Problem rating is calculated as the mean of the scores on three ten-point scales assessing the extent to which Hot Flushes/Night Sweats are problematic, distressing and causing interference in daily life. Scores for the problem rating range between 1 and 10, with higher scores indicating more problematic Hot Flushes/Night Sweats. The HFRS has been found to have reasonable test–retest reliability and good concurrent validity.
2. Menopause rating scale: The Menopause Rating Scale (MRS) is a questionnaire that assesses the presence and intensity of 11 menopausal symptoms. These are grouped into three subscales: the somatic subscale: assessing hot flushes/sweating, heart discomfort, sleeping problems, and muscle and joint discomfort (items 1–3 and 4 respectively); the psychological subscale: assessing depressive mood, irritability, anxiety, and physical and mental exhaustion (items 4–7 respectively); and the urogenital subscale: assessing sexual problems, bladder problems and vaginal dryness (items 8– 10, respectively). Each of the 11 items can be rated by the participant

from 0 (not present) to 4 (1 ¼ mild, 2 ¼ moderate, 3 ¼ severe and 4 ¼ very severe). The scores obtained for each individual item are summed to provide the corresponding total subscale score. The sum of subscales scores provide the total MRS score. Higher scores are indicative of more severe symptoms. Indeed values above 8 (somatic), 6 (psychological), 3 (urogenital) and 16 (total MRS) were defined as severe.

The secondary outcomes assessed

1. Quality of life as measured by menorrhagia multi-attribute scale: which is designed to measure the effect of menorrhagia on six domains of daily life (practical difficulties, social life, psychological health, physical health, work and daily routine, and family life and relationships). Summary scores, which range from 0 (severely affected) to 100 (not affected)
2. Menstruation, by pictorial bleeding assessment chart
3. Haemoglobin levels were also measured at pre-treatment, 1, 3 and 6 months.
4. Adverse event (Breast pain, Headache, Acne, Alopecia, Migraine, Increase in body weight...)

Statistical analysis

Data analysis was performed by using SPSS (IBM SPSS Statistics for Windows, Version 20.0. Armonk, NY: IBM Corp.). A one-sample Kolmogorov–Smirnov test was performed to analyze the distribution of clinical variables. The frequency and percentage of the categorical variables and the mean, standard deviation of the continuous and ordinal variables were presented. The study groups were compared using One-way analysis of variance (ANOVA) test for parametric variables and the Kruskal Wallis H test for the non-parametric variables. Wilcoxon signed rank test was used for the comparison of the BAI and FSFI scores at the first visit and second visits. For all calculations, a p-value of <0.05 was considered statistically significant.

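### With three active groups and no untreated comparison, a first-to-second-visit test cannot show the effect of each treatment; conclusions should rest on between-treatment differences

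*Combined protocol and SAP*

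**What the plan says.** The title is "The Effect of Estradiol Valerate, Lng-IUD, and Micronized Progesterone Treatment On Health Quality of Patients with Heavy Menstrual Bleeding". The opening text says that women "were asked to participate in this comparative study" and that "patients who fulfilled eligibility criteria were recruited to one of the following 3 groups". The groups are "Women who were treated with estradiol valerate/dienogest regimen for heavy menstrual bleeding", "Women who were treated with LNG-IUD for heavy menstrual bleeding" and "Women who were treated with oral Micronized Progesterone 200 mg for heavy menstrual bleeding". No untreated or placebo group is listed, and no randomisation or other allocation method is described.

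On entry: "Women were eligible for entry if they had self-described heavy menstrual bleeding". The PBAC value of 100 appears only as background in the list of baseline characteristics. It is not an entry threshold.

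The primary outcomes are HFRS and MRS. The secondary outcomes are MM-AS, PBAC, haemoglobin and adverse events. The scales are scheduled at 1, 3 and 6 months. PBAC is also in the baseline list and haemoglobin has a pre-treatment value, but no pre-treatment measurement is stated for HFRS, MRS or MM-AS.

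Statistical analysis compares the groups by one-way ANOVA or Kruskal-Wallis. Its only test of change is a Wilcoxon signed rank test of BAI and FSFI "scores at the first visit and second visits". The 0.05 threshold applies to all tests.

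**The concern.** A title that asks for the effect of three treatments invites a statement about each of them. The only named method for change is a paired test within a group. Without an untreated group, a significant fall from first to second visit mixes any treatment effect with natural course, placebo response and regression to the mean.

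Regression to the mean matters where the outcome is close to the entry condition. Women enter because they report heavy bleeding, so part of a high baseline PBAC may be a bad cycle that would have eased anyway. MM-AS measures the impact of the same complaint. At stake is a report that calls each treatment effective on a test that an ineffective treatment could also pass.

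**Working it through.** **No figure to reproduce.** The documents give no sample size, SD, test-retest correlation or target difference. Everything below is illustration under stated assumptions, with zero treatment effect throughout.

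**Assumed inputs.** Share of women above the entry cut-off *p* = 0.1, 0.5, 0.8; cycle-to-cycle correlation *ρ* = 0.5, 0.7, 0.9; 20, 30 or 50 women per group.

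**Step 1: expected fall if selection is on the measured baseline score.** For a normal score, fall = (1 − ρ) × φ(c)/p in population SDs, where c is the cut-off.
- p = 0.1: φ(c)/p = 0.1755/0.1 = 1.755. Fall = 0.5 × 1.755 = 0.88 (ρ = 0.5), 0.53 (0.7), 0.18 (0.9).
- p = 0.5: 0.3989/0.5 = 0.798. Fall = 0.40, 0.24, 0.08.
- p = 0.8: 0.2800/0.8 = 0.350. Fall = 0.175, 0.105, 0.035.

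**Step 2: chance that the signed rank test shows false improvement on that score.** Simulation of 1,000 runs per setting, 30 women per group, two-sided 0.05, so 2.5% is nominal in the improvement direction.

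| Share p | ρ = 0.5 | ρ = 0.7 | ρ = 0.9 |
|---|---|---|---|
| 0.1 | about 100% | 97% | 50–53% |
| 0.5 | 61% | 37–39% | 15–17% |
| 0.8 | 14–16% | 10–11% | 6–7% |

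Over 20 to 50 women per group the range is about 4% to 100%.

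**Step 3: selection on self-report instead.** Let k be the correlation between the transient error in the woman's own description and that in her baseline cycle. The fall in step 1 is then multiplied by k. For p = 0.2, φ(c)/p = 0.2800/0.2 = 1.400; with ρ = 0.7 and k = 0.5 the fall is 0.5 × 0.3 × 1.400 = 0.21 SD. With 30 women, ρ of 0.7 to 0.9 and the top 20% to 50% entering, the two-sided rejection rate (nominal 5%) is 6–31% for k = 0.5, 5–10% for k = 0.25, and 4–6% for k = 0, where women describe their usual bleeding.

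**Step 4: outcomes not used for entry (HFRS and MRS).** With 30 women, false improvement is about 2–4% if their transient error is unrelated to bleeding, which is roughly nominal. It is 3–28% if that correlation is 0.3. These rates cover regression to the mean only; natural course and placebo response are not modelled and would come on top.

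**Step 5: haemoglobin.** Excluding symptomatic anaemia selects in the opposite direction. Assume mean 11.5, SD 1.3 and a hard cut at 10. The standardised cut is (10 − 11.5)/1.3 = −1.15, and the ratio of the density to the share retained is 0.205/0.876 = 0.234. The mean then moves down by (1 − ρ) × 0.234 × 1.3 = 0.09 (ρ = 0.7) to 0.03 (ρ = 0.9), away from improvement.

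**Step 6: comparison between groups.** Kruskal-Wallis on change across three groups selected the same way rejects in about 4–6.5% of runs in every setting, because a shared regression cancels.

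**The case against.** The strongest reply is that the plan does not commit the error. The paired test names only BAI and FSFI, so no before-after test of PBAC, MM-AS, HFRS or MRS is actually specified. The study calls itself comparative and plans between-group tests. No sentence says that efficacy will be concluded from within-group change. All of this stands, so the point is conditional: it applies once the study's own scales are put into that sentence, which is the obvious way to repair it.

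A reader might infer more: that a before-after test will show improvement even if no treatment works. Selecting the top 20% to 30% on the measured baseline, with correlation 0.5 to 0.8 and 30 or 50 women, does give rejection in 49% to 100% of simulated groups. The documents do not support that reading. Entry is by self-description with a regular cycle, no score cut-off is set, and step 3 shows that the selection mechanism drives the result.

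Nor do the documents support extending strong regression to the mean to the primary outcomes, since women are not selected on HFRS or MRS. For MM-AS, if the first visit is month 1, much of the regression may already have happened.

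Finally, between-group differences are not a safe refuge by themselves. With no allocation method described they may be confounded, and three active groups cannot establish the absolute effect of any one of them.

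**Conclusion.** The point holds as a limit on interpretation. The design can address differences between the three treatments but not the separate effect of each, and a significant paired test on any of the study's scales could not be attributed to treatment. Natural course and placebo response are enough for that conclusion on every scale. Regression to the mean is an additional source on PBAC, possibly on MM-AS, and weak or absent on HFRS and MRS unless those scores move with bleeding.

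The size of the false-improvement rate cannot be stated. It runs from near nominal to almost 100%, and it rests on selection mechanism, cycle-to-cycle correlation and group size, all of which are assumptions here. The near-nominal rate for the between-group test assumes that the groups were selected alike, which the documents do not establish.

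**What to change.** - Word the aim as a comparison of the three treatments.
- Rest conclusions on between-treatment differences with 95% intervals, adjusted for the pre-treatment value where one is collected. On the documents that means PBAC and haemoglobin.
- State that no allocation method is described and that these differences may therefore be confounded.
- Report within-group change as an estimate and interval without a p-value, and do not call it an effect of the treatment. Make this change together with replacing BAI and FSFI in the signed rank sentence, so that the correction does not introduce the problem.

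The cost is wording in the aim and the analysis section plus an adjusted comparison; no new data are needed. The downside is that the report can no longer claim from a before-after test that each treatment improves scores.

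### The only haemoglobin exclusion limit is in the wrong unit, the same sentence literally says every woman was prescribed iron, and follow-up haemoglobin is compared without baseline adjustment

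*Combined protocol and SAP*

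**What the plan says.** All references are to the combined protocol and SAP.

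- **End of the description of the three treatment groups:** "None of the recruited patients were not prescribed oral iron preparations and patients who were symptomatic because of anemia (hb<10 mg/dl) were excluded".
- **Exclusion criteria, item 2**, the only laboratory item among the 13: "laboratory abnormalities (follicle stimulating hormone level higher than 40 iu/l, adverse endometrial histology". No numbered item gives a haemoglobin limit or mentions iron treatment.
- **Secondary outcomes, item 3:** "Haemoglobin levels were also measured at pre-treatment, 1, 3 and 6 months".
- **Allocation:** "patients who fulfilled eligibility criteria were recruited to one of the following 3 groups". No randomisation is described.
- **Baseline list:** it begins "Baseline characteristics of women are age (years), body mass index, parity, current smoker, days of bleeding, length of cycle (days" and goes on to bleeding, pain, the pictorial chart score and uterine measurements. Haemoglobin is not in it, although the opening section says it was among the blood tests.
- **Statistical analysis:** "The study groups were compared using One-way analysis of variance (ANOVA) test for parametric variables", with Kruskal-Wallis for non-parametric variables. No baseline covariate is mentioned.

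**The concern.** One sentence carries both an eligibility limit and a rule on concomitant treatment, and neither can be applied as written. The haemoglobin limit is in a unit that makes the number impossible. The iron statement, read literally, says the reverse of what was probably meant. Nothing elsewhere in the document corrects either.

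The stake is the interpretation of haemoglobin. If all women were prescribed iron, a rise after treatment reflects iron as well as any reduction in bleeding. If none were, the rise is easier to attribute to reduced bleeding. A reader also needs to know who was kept out for anaemia in order to judge the starting level.

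A separate weakness concerns the same outcome. Without random allocation, the groups may start at different haemoglobin levels. An unadjusted comparison at 1, 3 or 6 months carries part of that difference forward.

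**Working it through.** **1. Unit.** Input: the printed limit, 10 mg/dl. Since 1 g/dl = 1,000 mg/dl, 10 / 1,000 = 0.01 g/dl. The evident intent, 10 g/dl, is 10,000 mg/dl, and 10,000 / 10 = 1,000 times the printed figure. For an assumed range of 3 to 14 g/dl in living patients, values run from 3,000 to 14,000 mg/dl. None is below 10 mg/dl.

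**2. What each reading of the exclusion does.** The relevant words are "patients who were symptomatic because of anemia (hb<10 mg/dl) were excluded". Four illustrative patients (haemoglobin in g/dl):

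| Patient | Printed number applied strictly | Symptoms and Hb <10 g/dl | Hb <10 g/dl alone | Symptomatic anaemia, number ignored |
|---|---|---|---|---|
| 9.5, symptoms | kept | excluded | excluded | excluded |
| 9.5, no symptoms | kept | kept | excluded | kept |
| 10.5, symptoms | kept | kept | kept | excluded |
| 10.5, no symptoms | kept | kept | kept | kept |

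The second reading is the plain one once the unit is corrected, because the clause is about symptomatic patients. These are types of patient, not frequencies. The document gives no basis for saying how many women fall in each row.

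**3. Iron wording.** To say that none were not prescribed iron is to say that all were. Removing one negative gives the opposite: none were prescribed it.

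**4. Iron and the group comparison.** Let iron raise haemoglobin by an additive amount d, and let p1 and p2 be the proportions taking it in two groups. The between-group bias is d × (p1 − p2).

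- All women on iron: d × (1 − 1) = 0.
- No women on iron: d × (0 − 0) = 0.

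Both readings give zero for any d. A non-zero bias needs unequal use, which neither reading states, or an iron effect that differs between treatments.

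**5. Baseline haemoglobin (separate point).** If two groups differ by D before treatment and follow-up haemoglobin regresses on baseline with slope b, an unadjusted follow-up comparison carries b × D. The document gives neither quantity. Taking D = 0.5 g/dl purely as an assumption:

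- b = 0.3: 0.3 × 0.5 = 0.15 g/dl
- b = 0.5: 0.5 × 0.5 = 0.25 g/dl
- b = 0.7: 0.7 × 0.5 = 0.35 g/dl

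If the groups start level, the carried-over amount is zero and the adjustment serves only to improve precision.

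**The case against.** The strongest reply is that these are slips of drafting. Any clinician will read 10 g/dl, nobody would screen at 10 mg/dl, and the number is a parenthesis attached to a clinical criterion that works without it. Most of this stands. A reader might infer from the unit that the anaemia exclusion removes nobody. The document does not support that, because symptomatic anaemia remains a usable criterion whatever unit is printed. What remains is that the one stated limit is wrong and is corrected nowhere.

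A reader might also infer that the iron wording biases the comparison of the three treatments. That does not follow either: both readings apply one rule to every group. Unequal use despite a uniform prescribing rule is possible, but it would be a different concern and would survive perfect wording.

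It can be said, too, that the plain wording already requires symptoms, so only tighter drafting is needed there. That is fair. The reading based on haemoglobin alone leaves the word symptomatic with nothing to do, and a short clarification is enough.

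Finally, baseline adjustment has nothing to do with a unit or a double negative. That is correct, and it is offered as a separate improvement to the same secondary outcome. It rests on the allocation and analysis text. It does not rest on the absence of a paired haemoglobin test. The only paired test described is this: "Wilcoxon signed rank test was used for the comparison of the BAI and FSFI scores at the first visit and second visits". Those two scales are not among this study's listed outcomes, so that sentence is weak evidence of what was planned.

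**Conclusion.** The point holds and is minor. The only haemoglobin exclusion limit is wrong by a factor of 1,000, with 10 g/dl evidently meant. The iron statement literally says that all women were prescribed iron, and probably means that none were; the document does not confirm that intent. The consequence is limited to eligibility and to how haemoglobin changes are interpreted. Between-group bias from iron is zero under either uniform reading, assuming that use follows the stated rule and that the effect is additive.

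The unadjusted comparison of follow-up haemoglobin is a separate weakness of a group comparison without described randomisation. Its size depends on a baseline difference that the document does not report; the 0.15 to 0.35 g/dl in the working is an illustration only. Adjustment deals with differences in starting haemoglobin, not with other differences between the groups. The primary outcomes, the hot flush and menopause rating scales, are not shown to be affected.

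**What to change.** **Correct the sentence.** For example: *Patients with symptoms of anaemia and Hb <10 g/dl were excluded. No recruited patient was prescribed oral iron.* If the exclusion is meant to rest on haemoglobin alone, drop the reference to symptoms. If iron was in fact prescribed to all, say that. Where iron use was recorded, a description by group would help the reader. Iron started after treatment began should not be a covariate, because it may be a consequence of treatment.

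**Improve the haemoglobin analysis.** Compare follow-up haemoglobin between groups in a linear model with treatment group and pre-treatment haemoglobin, in place of the unadjusted test alone. Add pre-treatment haemoglobin by group to the baseline table.

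**Cost.** Rewording of one sentence, one row in the baseline table and one covariate in a secondary analysis. Haemoglobin is already measured at every time point needed, so no new blood tests are required.

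### The choice between ANOVA and Kruskal-Wallis is left, by implication, to a Kolmogorov-Smirnov pretest whose correction and application are not stated; name one analysis per outcome in advance

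*Combined protocol and SAP*

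**What the plan says.** The Statistical analysis section of the combined protocol and SAP gives the pretest in one sentence: "A one-sample Kolmogorov–Smirnov test was performed to analyze the distribution of clinical variables". The groups are then compared by "One-way analysis of variance (ANOVA) test for parametric variables and the Kruskal Wallis H test for the non-parametric variables". The significance rule is general: "For all calculations, a p-value of <0.05 was considered statistically significant". The software is SPSS 20.0, but no procedure or option is named.

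The section does not say:
- that the Kolmogorov-Smirnov (KS) result decides which variables count as parametric, although no other criterion is offered;
- which reference distribution is used, or whether the p-value allows for a mean and SD estimated from the same data;
- whether the test is run on pooled data, within each arm or on residuals;
- which outcome goes to which test.

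There are three treatment groups. Both primary outcomes are bounded scores. For the Hot Flush Rating Scale (HFRS), "Scores for the problem rating range between 1 and 10, with higher scores indicating more problematic Hot Flushes/Night Sweats". The Menopause Rating Scale (MRS) has 11 items scored 0 to 4, so its total runs from 0 to 44. Both are assessed at 1, 3 and 6 months. No sample size, effect size or outcome distribution is stated anywhere.

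**The concern.** The ordinary one-sample KS p-value is valid only against a fully specified distribution. If the mean and SD are estimated from the sample being tested, the fitted curve lies too close to the data and the test becomes very conservative. A pretest meant to detect non-normality would then often pass skewed scores on to ANOVA.

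A second problem remains even with a corrected p-value. The outcome data would still pick the primary test. ANOVA compares means and Kruskal-Wallis compares ranks, so a change of test changes the question answered. Two primary scales at three visits make six primary comparisons, and none has a test fixed in advance. At stake are power and a defined primary analysis, not false-positive control.

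**Working it through.** There is no stated figure to reproduce, so the behaviour of the rule was simulated.

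**Inputs from the document:** three groups; KS pretest, then ANOVA or Kruskal-Wallis; alpha 0.05, read as applying to the pretest too.

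**Assumed inputs:** 20 to 100 per equal group; skewness from 0 to about 6; one arm different from the other two by 0.58 SD with 30 per group, which gives ANOVA about 60% power for normal data.

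**Rule:** standardise by the sample mean and SD and compute the KS statistic. If the uncorrected asymptotic p<0.05 use Kruskal-Wallis, otherwise ANOVA.

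**Step 1: how often the uncorrected pretest rejects.** For normal data it rejects in 0.00 to 0.05% of samples (n=20 to 300), against a nominal 5%. For other shapes:

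| Distribution | n=30 | n=50 | n=90 | n=150 |
|---|---|---|---|---|
| Gamma k=4, skewness 1.0 | 0.3% | 1.5% | 5.8% | 19% |
| Gamma k=2, skewness 1.4 | 1.7% | 6.3% | 27% | 66% |
| Exponential, skewness 2 | 9.4% | 33% | 86% | 99.9% |
| MRS-like total | 0.6% | 3.2% | 22% | 67% |
| HFRS-like, 40% at floor | 29% | 76% | 99.8% | 100% |

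With a Lilliefors correction, rejection under normality returns to about 5%. For skewness 1.4 it rises to 47% at n=30 and 93% at n=90.

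**Step 2: power with 30 per group (pooled n = 3 × 30 = 90).** The last column is the rule with a pooled pretest minus Kruskal-Wallis, in points.

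| Scenario | ANOVA | Kruskal-Wallis | Rule, pooled | Rule, per arm | Difference |
|---|---|---|---|---|---|
| Gamma k=4, shift | 62.9 | 69.5 | 63.3 | 63.1 | −6.2 |
| Gamma k=2, shift | 61.0 | 77.0 | 64.3 | 62.4 | −12.7 |
| Exponential, shift | 63.7 | 90.9 | 81.2 | 72.8 | −9.7 |
| MRS-like | 59.2 | 62.1 | 59.5 | 59.3 | −2.6 |
| Lognormal 0.5, proportional | 58.1 | 59.4 | 58.5 | 59.4 | −0.9 |
| Gamma k=4, proportional | 63.9 | 56.4 | 62.9 | 64.0 | +6.5 |
| Exponential, proportional | 62.5 | 47.3 | 47.6 | 60.4 | +0.3 |

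In the gamma k=2 shift case the pooled pretest rejected in 16.0% of trials, so ANOVA was used in 100 − 16 = 84%. That is why the rule's power sits near ANOVA's. A separate simulation with a 0.5 SD shift gave 54% for the rule against 66% for Kruskal-Wallis, a gap of 12 points.

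**Step 3: effect of the unstated implementation.** For exponential data, pooled against per-arm pretesting gives 81.2% against 72.8% power for a shift (8.4 points) and 47.6% against 60.4% for a proportional effect (12.8 points the other way). The text permits either.

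**Step 4: different tests at two visits.** If the pretest rejects with probability p at each of two visits, and the visits are treated as independent, the tests differ with probability 2p(1 − p). For the MRS-like score:
- pooled n=90, p=0.22 with no group difference: 2 × 0.22 × 0.78 = 0.34;
- pooled n=90, p=0.082 with an effect in one arm: 2 × 0.082 × 0.918 = 0.15;
- pooled n=150, p=0.67 with no group difference: 2 × 0.67 × 0.33 = 0.44;
- pooled n=150, p=0.439 with an effect in one arm: 2 × 0.439 × 0.561 = 0.49.

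Positive correlation between visits would lower these figures.

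**The case against.** The strongest case against the point is that much of it rests on what the plan does not say.

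- **Use of an uncorrected p-value.** The document names SPSS and a one-sample KS test but not the procedure, so a corrected version is possible. This stands, and the statements about size and missed skew are therefore conditional. It does not remove the selection problem.
- **KS as the selector.** This is implied, not written. That stands too, but the section offers no other way to decide which variables are parametric.
- **Tests differing by visit.** The text classifies variables, not visits, so the investigators may mean one decision per scale. That is possible. Nothing says so, and nothing says at which visit such a decision would be made.
- **Testing the outcome and not residuals.** Per-arm testing would largely meet this objection, and the text does not exclude it.
- **Size.** The largest losses come from unbounded variables with a pure location shift. The loss is under 3 points for MRS-like data with 30 per group. An HFRS-like score with 40% at the floor goes to Kruskal-Wallis in 99.8% of samples at n=90, so almost nothing is lost. With 100 per group and a pooled pretest, the rule is within 1 point of Kruskal-Wallis in every skewed case except gamma k=4. All of this stands.

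A reader might infer that the pretest almost never rejects and so costs power across the board. The calculations do not support that. Strong skew is usually detected at a pooled n of about 90, and ANOVA is the stronger test for proportional effects in gamma or exponential data. A reader might also infer that the plan wants rank tests for the skewed scores. The section assigns no outcome to either test.

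**Conclusion.** The point holds in a limited form. By implication the plan lets a normality pretest on the outcome data choose the group comparison, and it leaves the correction and the mode of application open. If the p-value is uncorrected, the pretest's true size is near 0% and it usually misses moderate skew (about 1 to 1.75) in small samples.

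The consequence for power has no fixed direction. With 30 per group and a pooled pretest, the difference from Kruskal-Wallis ranges from a loss of 12.7 points to a gain of 6.5 points over the scenarios examined. Type I error is not the issue. The more robust part of the finding is that no primary comparison has a test fixed in advance, so the same scale could receive different tests at different visits.

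The magnitudes rest on assumed group sizes, distributions and effects and cannot be derived from the document. The change is worth making because it is cheap, but confidence in the size of the benefit is only moderate.

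**What to change.** Remove the KS test as a selector. In the Statistical analysis section:

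1. Name one analysis for each outcome and use it at 1, 3 and 6 months. Choose it from the nature of the scale and the kind of effect expected. Neither a rank test nor a comparison of means is best for every effect.
2. Adjust for baseline where the plan records one. That is haemoglobin, which has a pre-treatment measurement, and the PBAC score, which is among the baseline characteristics. HFRS, MRS and MM-AS are not in the baseline list and are scheduled only at 1, 3 and 6 months. Adjust those only if a pre-treatment score was in fact taken.
3. If a normality check is kept, apply a Lilliefors-corrected or Shapiro-Wilk test to model residuals. Report it as a diagnostic that does not change the primary test.

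The cost is a few sentences. No extra patients are needed, and no new data for haemoglobin and PBAC. The same cannot be promised for adjusting the three questionnaires. The remaining downside is that the fixed test may not be the most powerful one for the effect that occurs. With 30 per group, for example, Kruskal-Wallis trailed ANOVA by 63.9 − 56.4 = 7.5 points for a proportional effect in gamma (k=4) data.
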